## **STUDY PROCEDURES**

### **Procedure for informing and obtaining consent**

Patients or subjects can only be enrolled in the study after written informed consent has been obtained. The written informed consent requires an oral and written explanation to the patients/subjects, as well as their parents or legal guardians, about the aims and methods (incl. scientific-explorative character of the study), benefits and risks as well as the revocability of the study participation. Children and adolescents are informed by means of age-appropriate, comprehensible patient information sheets. By giving written informed consent, the patients/participants as well as their parents/guardians declare that they agree with the collection and storage of study-relevant data and their review by monitoring or authorities. It must be clearly conveyed to the study participant that withdrawal of consent is possible at any time and without any disadvantage. Furthermore, all study participants/subjects and parents/guardians are informed that this study is a purely scientific study without any current diagnostic or therapeutic benefit. In case of incidental findings, the study participants/test persons and parents/guardians will be informed and further clarification will be initiated if indicated.

The original consent form will be kept in the study folder at the study site. The patient/proband and parent/guardian will be given a copy of the patient information and consent form. The patient information and informed consent form can be found in the appendix of this study protocol.

### **Measures and recording the target values**

Together with the patient and the patient's family, a date for the study is set. After the patient has been informed about the study by phone or in person at least one day in advance, a routine blood sample is taken through a venous access during the chemotherapy or follow-up visit. Patients currently undergoing treatment will already have a venous access used for chemotherapy (CVC or Hickman catheter or port catheter). This can then be used for the study-related contrast agent, so no additional intervention is required. The region to be examined in all patients is one kidney and its immediate surroundings. Patients can lie relaxed during the scan.

### **Timing and duration of the study**

Patients will be examined using ULM during an outpatient or inpatient stay for chemotherapy or aftercare. A total of 30 patients will be included in the study.

The expected duration of the study for individual patients is 30 minutes to 1 hour.

**Total duration of the study**

The expected total duration of the study is 18 months.

## **RISK-BENEFIT-ANALYSIS**

### **Study-related risks with ULM**

#### ***Insertion of a peripheral venous catheter (pVK)***

For the examination using ULM in the 20 individuals who have completed treatment for ALL and are seen during aftercare it is necessary to insert a peripheral venous catheter (pVK) (e.g. in the hand, crook of the elbow). The insertion of a peripheral venous catheter is generally feasible without limitations even in children after completion of chemotherapy. For this study, catheter placement will be combined with routine blood sampling to avoid additional burden. As with any blood sampling, this can result in injury to the skin at the entry point. There is also a risk of infection at the entry site, but this is very low given the short time of insertion of approx. 2 hours.

In the 10 individuals who will be assessed before therapy day 50 (Visit 1) and after completion of intensive chemotherapy (Visit 2), the routinely implanted central venous catheter will be used for the administration of the contrast agent. In these cases, no additional pVK is required. Laboratory chemistry parameters (including BB, Diff, Glucose, Na, K, Cl, Ca, LDH, Crea, Cystatin C, Uric Acid, CRP, Albumin, Ferritin, Total Protein) and urinalysis including urinary status, proteinuria/haematuria as well as conventional ultrasound assessment are routinely performed during therapy and aftercare. So, in addition to ULM, no extra procedure will be undertaken in the frame of this study.

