#### *Primary outcome measures collected by ULM*

ULM: Visualisation of the microvascular architecture of the kidney

- ULM: Quantification of perfusion dynamics in one kidney (including measurement of peak enhancement (PE), wash-in area under the curve (WIAUC), wash-in perfusion index (WiPI), wash-in rate (WIR), wash-out area under the curve (WoAUC), wash-in and wash-out area under the curve (WiWoAUC), wash-out rate (WoR), time to peak (TTP), rise time (RT), mean transit time (local) (mTTI) and fall time (FT)).

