#### ***Contrast agent application***

A contrast medium (SonoVue®) is administered venously, a potential intolerance to the contrast medium (allergic reaction) is a possible however very low risk of this study. It is an already established contrast agent the tolerability of which has been investigated in several studies: In a large study, 23,188 patients examined showed a rate of 0.0086% 'adverse events' (18). In a separate investigation, 30,222 patients were examined, with a rate of 0.02% (19). The adverse events included self-limiting symptoms such as redness, epistaxis, vomiting, nausea, back pain, numbness and symptoms of incipient anaphylaxis (18, 19).

In our working group, children have already been examined several times using ULM and SonoVue contrast enhancement.

The information for healthcare professionals on SonoVue reports very rare cases of reactions with fatal outcome that were temporally related to the use of SonoVue®. Notably, the patients concerned were already at high risk of cardiac complications.

Repeated applications during an examination are permitted, overdoses have not been described. SonoVue® has no drug approval for this examination or intravenous use in children and will be used off-label. SonoVue® is not nephrotoxic, remains intravascular, and is

eliminated via the lungs and phospholipid metabolism. It can be safely administered even in patients with impaired renal function.

The ULM measurements are performed using a CE certified clinical ultrasound system.

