### **Calculation of case numbers**

As this is a pilot study and no information is yet available on the expected differences between the different groups, no calculation of the number of cases has been made. The number of cases given is an estimate.

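### Contrast access route coincides completely with cohort, so an early-versus-late difference in the wash-in/wash-out primary outcomes cannot be attributed to the kidney alone

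*Protocol*

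**What the plan says.** **Route.** Under Insertion of a peripheral venous catheter (Risk-Benefit-Analysis), the protocol states for the 10 early-cohort patients, at both visits, that "the routinely implanted central venous catheter will be used for the administration of the contrast agent". For the 20 aftercare patients the same section says "it is necessary to insert a peripheral venous catheter (pVK) (e.g. in the hand, crook of the elbow" are the examples given). Under Measures and recording the target values, the central access is not of one kind: "Patients currently undergoing treatment will already have a venous access used for chemotherapy (CVC or Hickman catheter or port catheter").

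**Outcomes.** Primary outcome measures collected by ULM lists visualisation of the microvascular architecture and 11 perfusion parameters. These are peak enhancement, wash-in and wash-out areas and rates, a perfusion index, and times such as "time to peak (TTP), rise time (RT), mean transit time (local) (mTTI) and fall time (FT").

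**Comparison.** The primary objective covers the kidney across all phases of leukaemia treatment. Calculation of case numbers says that "no information is yet available on the expected differences between the different groups". Statistics names Mann-Whitney or ANOVA at the 0.05 level, without saying which groups are compared. None of these sections mentions the difference in route as a limitation or as something the analysis must deal with.

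**The concern.** Wash-in and wash-out parameters describe contrast arriving in the kidney and leaving it again. They reflect the kidney, but they can also reflect the path and speed by which contrast gets there. Contrast given into a hand or elbow vein has to pass through the arm veins first; contrast given through a central catheter does not. The two cohorts could therefore show different curves even with the same renal microvasculature. A route effect in the opposite direction could equally hide a real renal difference.

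The stake is what the pilot hands on. Under Number of patients, the study is meant to supply effect sizes for larger studies. Under Study related benefits, ULM differences are envisaged as future predictors of nephropathy. There is no healthy or untreated control group, so the early cohort is the only internal comparator for the survivors. A route artefact in that comparison would be carried forward as a renal effect.

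**Working it through.** **1. The plan's own figures.** Patients: 10 + 20 = 30. Examinations: 10 × 2 + 20 × 1 = 40. Both agree with Number of patients. No power, effect size or SD is stated, so there is nothing else to reproduce.

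**2. Route and cohort side by side.**

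| Cohort | Patients | Visits | Central | Peripheral |
|---|---|---|---|---|
| Early | 10 | 2 | 10 | 0 |
| Late | 20 | 1 | 0 | 20 |

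Write a perfusion value as y = μ + β·(late cohort) + γ·(peripheral route) + error. The two indicators are identical in all 30 patients, so the early-versus-late difference estimates β + γ. A model containing both terms cannot be fitted, because no cohort supplies information on γ.

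In the Timepoint 1 versus Timepoint 2 comparison, both examinations use central access and γ cancels. Only a change of central catheter type between visits could remain.

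**3. Is the comparison foreseen?** Mann-Whitney is a test for independent groups. The only independent groups that the protocol defines are the 10 and the 20, and Calculation of case numbers speaks of differences between groups. The comparison is implied, not named.

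**4. How much could it matter?** The documents give no route effect, so a range is assumed. Inputs: n₁ = 10, n₂ = 20, level 0.05 taken as two-sided (the protocol does not say), normal data, β = 0, and a route-only shift of d SDs.

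- t-test: noncentrality δ = d / √(1/10 + 1/20) = d / 0.387, with 28 degrees of freedom. For d = 0.5, δ = 1.29 and the rejection probability is 23.9%.
- Mann-Whitney: 20,000 simulated studies per row. The simulation standard error is at most √(0.25/20,000) = 0.35 percentage points.

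| Assumed route-only shift (SD) | δ | t-test significant | Mann-Whitney significant |
|---|---|---|---|
| 0 | 0 | 5.0% | 4.4% |
| 0.25 | 0.65 | 9.6% | 8.5% |
| 0.5 | 1.29 | 23.9% | 21.6% |
| 0.75 | 1.94 | 46.4% | 42.0% |
| 1.0 | 2.58 | 70.3% | 65.5% |
| 1.5 | 3.87 | 96.2% | 94.6% |

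For scale, the smallest true difference that a t-test of 10 versus 20 detects with 80% power is about 1.12 SD. The normal approximation gives (1.960 + 0.842) × 0.387 = 1.085.

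**The case against.** The strongest reply is that the protocol never says its late-effect conclusion rests on testing survivors against the early cohort. The study flow sets early and late effects in separate columns, the primary objective is to visualise and quantify, and the secondary objectives are correlations. This stands: the comparison is an inference from the wording on groups and from the choice of test. It is still the natural reading, and nothing in the protocol excludes it.

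Second, the cohorts differ in other ways. They are not randomised, they are at different treatment phases, and only the late cohort excludes known clinically evident renal impairment. The contrast could not be read causally even with one route. This also stands, and it favours descriptive reporting. Route remains worth naming separately because it can act on the measurement itself, whatever the state of the kidney.

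Third, this may look like detail for an analysis plan or imaging manual. That does not hold for the core of the point. The protocol itself fixes the routes, no later plan can adjust for them, and access type has to be recorded when the examination is done.

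A reader might go further in three ways that the documents do not support:

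- That the outcomes do differ because of route. The documents give no size, direction or evidence of such an effect, and do not describe the mode of injection.
- That repeat contrast adds to the cohort difference. The sentence "Repeated applications during an examination are permitted" stands in the risk section and is not limited to one cohort. It may add variability, but it shows no difference between cohorts.
- That the chance of a false finding should be accumulated over all 11 parameters. Such a figure would mix in multiplicity, which exists without any route effect, and would need the same shift in every parameter.

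**Conclusion.** The point holds in a limited form. Access route and cohort are the same variable in this design, so a raw early-versus-late difference in any of the 11 perfusion parameters cannot be separated from a route effect, and no covariate adjustment can change that. This follows from the protocol's own text.

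The size is unknown. Under the assumptions above, false significance for a single parameter runs from about 9% at a shift of 0.25 SD to about 66% at 1.0 SD, against a nominal 5%. These percentages show how sensitive the comparison is; they do not predict what will happen. That a route effect is possible at all rests on what wash-in/wash-out parameters measure, which the protocol does not discuss.

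The within-patient comparison in the early cohort does not carry the central-versus-peripheral difference. Whether the architecture outcome is free of it cannot be settled from the documents. The background section says the map is built by accumulating microbubble tracks, so delivery might matter there too, and moving the early-versus-late test to that outcome is not a proven remedy.

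**What to change.** In Statistics, state that:

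- significance testing of the perfusion parameters is confined to Timepoint 1 versus Timepoint 2 within the early cohort, with a method for paired data (Mann-Whitney treats the samples as independent);
- early-versus-late perfusion differences are reported descriptively, with a sentence that access route coincides with cohort, and are not passed on as effect sizes attributed to the kidney alone;
- where an artery is visible in the same clip, an artery-referenced value may be added as a supportive analysis.

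For each examination, record the access type (kind of central catheter, or peripheral site) and the number of contrast applications. How contrast is given stays unchanged.

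The cost is a few sentences and two recorded fields, plus one extra region of interest wherever the optional arterial reference is used. The real price is that there is no confirmatory early-versus-late test of the perfusion parameters, and the tested comparison rests on 10 patients.

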#### ***Contrast agent application***

A contrast medium (SonoVue®) is administered venously, a potential intolerance to the contrast medium (allergic reaction) is a possible however very low risk of this study. It is an already established contrast agent the tolerability of which has been investigated in several studies: In a large study, 23,188 patients examined showed a rate of 0.0086% 'adverse events' (18). In a separate investigation, 30,222 patients were examined, with a rate of 0.02% (19). The adverse events included self-limiting symptoms such as redness, epistaxis, vomiting, nausea, back pain, numbness and symptoms of incipient anaphylaxis (18, 19).

In our working group, children have already been examined several times using ULM and SonoVue contrast enhancement.

The information for healthcare professionals on SonoVue reports very rare cases of reactions with fatal outcome that were temporally related to the use of SonoVue®. Notably, the patients concerned were already at high risk of cardiac complications.

Repeated applications during an examination are permitted, overdoses have not been described. SonoVue® has no drug approval for this examination or intravenous use in children and will be used off-label. SonoVue® is not nephrotoxic, remains intravascular, and is

eliminated via the lungs and phospholipid metabolism. It can be safely administered even in patients with impaired renal function.

The ULM measurements are performed using a CE certified clinical ultrasound system.

### **Study related benefits**

The data obtained in this study may provide important insights into the acute and chronic nephrotoxicity of ALL therapy. The potentially quantifiable differences in ULM could be used in the future as markers to predict nephropathy. Follow-up methods and measures, schedules and treatment plans could be adapted.

### **Withdrawal criteria**

Withdrawal criteria are an allergic reaction to the ultrasound contrast agent and reddening or warming of the skin during optoacoustic imaging.

The entire study will be stopped if a reassessment of the expected and unexpected side effects of the drugs or devices used indicates an increased risk to the subjects.

### **Statement on medical justifiability**

Based on experience to date, the risk of adverse events is considered to be extremely low.

With ULM, the rate of side effects is very low and if they do occur, they are rapidly reversible and easily treatable.

Given the current lack of diagnostic tools and data on post-chemotherapy nephrotoxicity, we assume this method will provide new diagnostic tools that will significantly improve long-term follow up care in the future.

### **Calculation of case numbers**

As this is a pilot study and no information is yet available on the expected differences between the different groups, no calculation of the number of cases has been made. The number of cases given is an estimate.

### **Statistics**

The data is given as a mean value with standard deviation. Correlations are indicated with the non-parametric Spearman correlation coefficient (Rs). Differences in the mean values are analysed statically using a non-parametric T-test (Mann-Whitney test) or ANOVA. In all analyses, an error level of <0.05 is considered statically significant.

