## **OBJECTIVES**

### **Hypotheses**

- ULM can be used to visualise and quantify the microvascular perfusion dynamics in the kidney and differs depending on the organ function
- Treatment of acute lymphoblastic leukaemia leads to (often subclinical) acute and chronic impairment of renal function also through vascular injury which can be visualized by ULM.

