### **Study arms: interventional/control**

Patients fulfilling the inclusion criteria will receive ULM of one kidney. Patients with recently diagnosed ALL will receive ULM at two timepoints whereas participants in the oncological follow up after treatment for ALL will be examined at a single visit.

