### Graphical design of study flow

**Figure 1: Course of Study**

**STUDY POPULATION / IN- AND EXCLUSION CRITERIA**

Early therapeutic effects	Late therapeutic effects
Planned number of patients	
N = 10 ALL (recently diagnosed ALL)	N = 20 ALL (completed oncological treatment)
Planned number of examinations for each participant	
2 (before first CPM according to therapy protocol and after completion of intensive therapy)	1
Inclusion criteria	

 
- Diagnosed acute lymphatic leukemia
 
- Treatment day < 50 according to therapy protocol / no administration of CPM before first examination
 
- From 3 years to < 18 years
 
	
 
- Diagnosed acute lymphatic leukemia
 
- Completed oncological treatment
 
- From 3 years to < 18 years
 

Exclusion criteria	

 
- Known allergic disposition to SonoVue / other contrast agents
 
- Tattoo in the area of the examination field
 
- Pregnancy
 
- Breastfeeding mothers
 
- Contraindication for the use of Sonovue
 
- Critical condition
 
	
 
- Known clinically evident renal impairment
 
- Known allergic disposition to SonoVue / other contrast agents
 
- Tattoo in the area of the examination field
 
- Pregnancy
 
- Breastfeeding mothers
 
- Contraindication for the use of Sonovue
 
- Critical condition
 

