**Number of patients**

As this is a pilot study, it is not possible to calculate the exact number of patients. It is planned to include 30 patients (in total 40 examinations). The planned sample size of 30 participants (10 during therapy and 20 in follow-up) was determined based on the annual incidence of ALL at our center, which is approximately 15 cases per year. Recruitment within the intended timeframe of 12–18 months is therefore considered feasible. In addition, the study has a pilot character, aiming to provide the first data set for estimating effect sizes and to serve as a foundation for the design of larger subsequent studies. 10 patients who will undergo an ULM examination of the kidney before the start of chemotherapy, latest before therapy day 50 before the first application of high-dose methotrexate or cyclophosphamide (Timepoint 1). After completion of intensive therapy (after administration of cyclophosphamide and high-dose methotrexate), they will receive a follow-up ULM

Contents are confidential. No disclosure to third parties.

examination (Timepoint 2) approx. 6-9 months after the first ULM examination. In addition, 20 different patients who have completed treatment for ALL and are seen during aftercare will be included in the study.

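### The before/after comparison in the 10 newly diagnosed children is paired, but the only two-sample test the protocol names is for independent groups

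*Protocol*

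**What the plan says.** For differences, the Statistics section of the protocol gives one sentence: "Differences in the mean values are analysed statically using a non-parametric T-test (Mann-Whitney test) or ANOVA". It adds that "In all analyses, an error level of <0.05 is considered statically significant". Otherwise it provides for means with standard deviations and Spearman correlations. It does not say which test serves which comparison, and it does not say what form the ANOVA takes.

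The design has two cohorts. Under Study arms, "Patients with recently diagnosed ALL will receive ULM at two timepoints", while aftercare participants are seen once. The table under Study population sets the early cohort at 10 patients with two examinations each, the first before cyclophosphamide and the second once intensive therapy is complete. Number of patients places the second examination of these same children at "Timepoint 2) approx. 6-9 months after the first ULM examination", and adds 20 different patients from aftercare.

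The Hypotheses section states that "Treatment of acute lymphoblastic leukaemia leads to (often subclinical) acute and chronic impairment of renal function". The Primary objectives cover perfusion before, during and after treatment. Number of patients describes the study as "aiming to provide the first data set for estimating effect sizes" for larger studies to follow.

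**The concern.** Timepoint 1 against Timepoint 2 is the only comparison in the study in which each child serves as his or her own control. It bears most directly on the acute part of the hypothesis. The Mann-Whitney test treats the 20 measurements as if they came from 20 unrelated children. Stable differences between children (the protocol admits ages from 3 to under 18 years) then stay in the comparison as noise, although the design allows them to be removed. With only 10 pairs, a real change could be reported as non-significant.

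The pilot's stated purpose is also affected. A later before/after study needs the SD of the within-patient change to set its sample size. The Statistics section plans only means with SDs and does not ask for the change.

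**Working it through.** **Design count.** 10 × 2 + 20 × 1 = 40 examinations in 10 + 20 = 30 patients. This reproduces the totals under Number of patients and confirms 10 pairs plus 20 independent single examinations.

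**Which test fits which comparison.**
- Early cohort at one timepoint against the 20 aftercare patients: different children, so Mann-Whitney is suitable.
- Timepoint 1 against Timepoint 2: the same 10 children, so a paired method is needed and none is named.
- All three sets of examinations together: a one-way ANOVA would treat all 40 as independent, although 20 of them come from 10 children.

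**Why pairing matters.** Let σ be the SD at each timepoint, ρ the within-child correlation and n = 10. The variance of the mean change is 2σ²(1 − ρ)/n. An unpaired analysis works as if it were 2σ²/n. At ρ = 0.5 the figures are 0.10σ² and 0.20σ²; at ρ = 0.7 they are 0.06σ² and 0.20σ².

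**Inputs.** From the protocol: 10 pairs and a 0.05 level. Assumed, because the protocol gives no values: two-sided testing, normal data with equal SD at both timepoints, ρ from 0 to 0.8, and shifts of 0.5, 0.8 and 1.0 SD.

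**Power and false-positive rate.** Simulation with 100,000 replicates per setting and exact critical values: Mann-Whitney U ≤ 23 (nominal size 4.3%) and signed-rank W ≤ 8 (nominal size 4.9%). The middle columns give power for Mann-Whitney / Wilcoxon signed-rank.

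| ρ | 0.5 SD | 0.8 SD | 1.0 SD | Mann-Whitney rejections with no change |
|---|---|---|---|---|
| 0 | 16 / 16% | 35 / 35% | 51 / 50% | 4.4% |
| 0.3 | 13 / 22% | 33 / 46% | 52 / 64% | 1.9% |
| 0.5 | 10 / 28% | 32 / 60% | 53 / 78% | 0.8% |
| 0.7 | 8 / 43% | 31 / 81% | 55 / 94% | 0.2% |
| 0.8 | 6 / 59% | 31 / 93% | 57 / 99% | 0.1% |

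With no change, the signed-rank test rejects close to 5% at every ρ. A separate run of 20,000 replicates agreed to within about one percentage point. In that run, a one-way ANOVA on the paired data at 0.8 SD had 37% power at ρ = 0.5 and 35% at ρ = 0.7. The paired t-test had 62% and 83%.

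**Precision of the mean change.** Half-width of the 95% confidence interval, in SD units:
- Unpaired: t(18, 0.975) × √(2/10) = 2.101 × 0.447 = 0.94 at every ρ.
- Paired: t(9, 0.975) × √(2(1 − ρ)/10) = 2.262 × √(2(1 − ρ)/10), which gives 1.01, 0.85, 0.72, 0.55 and 0.45 at ρ = 0, 0.3, 0.5, 0.7 and 0.8.

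**The case against.** The protocol never assigns Mann-Whitney to the two timepoints, and the test has a proper use between the cohorts. ANOVA is also offered, and with two timepoints a repeated-measures ANOVA is equivalent to a paired t-test. The primary objective is visualisation and quantification, and the before/after comparison is not written out as a formal test. Matching tests to comparisons is often left to a statistical analysis plan. On this reading the point is a missing detail.

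The size of the loss rests on assumed values. The largest gaps need a correlation of 0.7 to 0.8 over 6 to 9 months of intensive chemotherapy in growing children, and nothing in the protocol supports a value that high. At correlations of 0 to 0.3 the gap for a 0.8 SD shift is nil to 13 percentage points. The error is conservative, this is a pilot without a power calculation, and the paired data will exist whatever test is named.

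Much of this stands. A repeated-measures ANOVA is not excluded, the loss may be modest, and the SD of the change can still be computed later. What does not stand is the missing-detail reading. The sentence covers differences in general and names a specific two-sample test that is wrong for the one within-patient comparison. An analysis plan that followed it would carry the error forward, and one that used a paired test would depart from the protocol.

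**Conclusion.** The concern holds. No suitable test is specified for Timepoint 1 against Timepoint 2, and using the only two-sample test named would analyse paired data as unpaired. Under positive within-child correlation the consequence is lost power and a true error rate well below 5%, not false positives. The size depends on a correlation, SD and effect that the protocol does not give: nothing is lost at correlation 0, and at an assumed 0.8 SD shift power falls by 28 percentage points at 0.5 (60% to 32%) and by 50 at 0.7 (81% to 31%). These figures show the direction and possible scale of the loss under normality and equal variances; they do not predict it for this study. No safety matter is involved, but the text should be corrected before analysis.

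**What to change.** Amend the Statistics section to state:

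1. Timepoint 1 against Timepoint 2 in the early cohort is analysed with a Wilcoxon signed-rank test (or paired t-test), and the within-patient change is reported with its SD and 95% confidence interval.
2. Mann-Whitney is used only between different patients, that is, the early cohort at a stated timepoint against the 20 aftercare patients.
3. If all three sets of examinations are analysed together, a mixed model with a patient random effect replaces one-way ANOVA. This item can be left out if only separate comparisons are planned.

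The cost is two or three sentences. No extra patients, examinations or procedures are needed.

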### **Secondary objectives**

- ULM: Correlation of the vascular architecture of the kidney **visualised** by ULM before, during and after treatment of acute lymphoblastic leukaemia (e.g. number of segmented glomeruli) with laboratory chemical parameters (including renal function parameters, inflammation parameters, immunological parameters)
- ULM: Correlation of vascular architecture of the kidney **visualised** using ULM before, during and after treatment of acute lymphoblastic leukaemia (e.g. number of segmented glomeruli) with sonographic parameters (e.g. resistance index (RI), flow velocity)
- ULM: Correlation of parameters of **quantified** microvascular perfusion dynamics of the kidney before, during and after treatment of acute lymphoblastic leukaemia with

laboratory chemical parameters (e.g. renal function parameters, inflammation parameters)

- ULM: Correlation of parameters of the **quantified** microvascular perfusion dynamics of the kidney before, during and after treatment of acute lymphoblastic leukaemia with sonographic parameters (including resistance index (RI), flow velocity)

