## **Recruitment**

Patients (and parents) will be informed about the possibility to participate in the study when visiting the pediatric clinic for hematology and oncology (including its outpatient clinics) or attending the follow-up consultation (Department for internal Medicine / Med 5 University Hospital Erlangen). If patients and their parents are interested to participate, they will be fully informed about the aims and methods (especially about the scientific/explorative nature of the study), the benefits and risks, and the revocability of participation in the study before giving their consent prior to study initiation. Patients in childhood and adolescence are additionally informed and educated about the study and its procedure in an age-appropriate manner.

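### The Statistics section calls every p below 0.05 significant, which fits poorly with an exploratory pilot that has at least 11 unranked primary parameters and aims to estimate effect sizes (minor)

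*Protocol*

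**What the plan says.** **Decision rule.** The protocol's Statistics section ends: "In all analyses, an error level of <0.05 is considered statically significant". The sentence has no exploratory qualifier. It covers Spearman correlations and the tests of differences: "Differences in the mean values are analysed statically using a non-parametric T-test (Mann-Whitney test) or ANOVA". The descriptive output of the section is the mean with its standard deviation.

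**What the rule is applied to.** Under Primary outcome measures collected by ULM, the second item begins "Quantification of perfusion dynamics in one kidney (including measurement of peak enhancement (PE), wash-in area under the curve (WIAUC" and goes on to name 11 parameters: PE, WIAUC, WiPI, WIR, WoAUC, WiWoAUC, WoR, TTP, RT, mTTI and FT. The list is introduced by the word for inclusion rather than closed, and no parameter is put first. The Secondary objectives add four families of correlations of ULM measures, such as the "number of segmented glomeruli", with laboratory and sonographic values. The number of these correlations is left open.

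**Purpose of the study.** Number of patients describes a pilot "aiming to provide the first data set for estimating effect sizes and to serve as a foundation for the design of larger subsequent studies". Families are told of its exploratory status: "especially about the scientific/explorative nature of the study" under Recruitment and "scientific-explorative character of the study" under Procedure for informing and obtaining consent. Calculation of case numbers states that no sample size was computed.

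**The concern.** The stated purpose is estimation; the stated analysis rule is a verdict. A pilot that is to inform later designs needs each effect with its uncertainty. The Statistics section instead asks for group means with standard deviations and then sorts results into significant and not significant at a single per-test level. The exploratory status given elsewhere is not carried into that rule.

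Two things follow if the rule is applied as written. First, with at least 11 primary parameters of equal standing, a chance finding in one of them may well be reported as significant on a primary outcome. Second, the effect sizes are reported without a measure of precision, although precision is what the designer of a later study needs most from 30 patients.

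**Working it through.** **Plan's own figures.** There is no power or sample-size calculation to reproduce. The counts are consistent: 10 + 20 = 30 patients and 10 × 2 + 20 × 1 = 40 examinations.

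**Inputs from the protocol.** Per-test level 0.05 (Statistics); 11 named primary perfusion parameters (Primary outcome measures); groups of 10 and 20, with two examinations in the group of 10 (Number of patients).

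**Assumptions, not in the protocol.** One comparison of 10 against 20 per parameter; two-sided tests; no true effect; a common pairwise correlation r between the 11 parameters. The protocol gives no correlations, so a range is shown.

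**Chance of at least one significant primary result**

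- Independent tests: 1 − 0.95^11 = 1 − 0.569 = 43.1%. Expected number of false positives: 11 × 0.05 = 0.55.
- Correlated tests: simulation of 11 equicorrelated normal test statistics, 400,000 draws per value of r. A second simulation used the exact Mann-Whitney test at 10 against 20. That test rejects when U ≤ 55 and has an exact size of 4.9%; 40,000 studies were simulated.

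| r (assumed) | Normal statistics | Exact Mann-Whitney |
|---|---|---|
| 0 | 43% | 42% |
| 0.5 | 30% | 31% |
| 0.8 | 18% | 20% |
| 0.9 | 13% | 14% |

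A third run, with the large-sample Mann-Whitney p-value and 4,000 studies, gave 39%, 29% and 13% at r = 0, 0.5 and 0.9. It is slightly lower at r = 0 because that version of the test is more conservative at these group sizes.

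The parameters are all read from the same enhancement curve, and some overlap by construction (wash-in area, wash-out area and their combination). Independence is therefore not credible, and 43% is an upper figure. The rows from 0.5 to 0.9 are the relevant ones.

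**Precision of the estimates the pilot can supply**

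- Difference, 10 against 20, 95% half-width in SD units: t(0.975; 28) × √(1/10 + 1/20) = 2.048 × 0.387 = 0.79 SD.
- Within-patient change, 10 pairs: t(0.975; 9) / √10 = 2.262 / 3.162 = 0.72 SD of the change.
- Spearman correlation, Fisher z with variance 1.06/(n − 3), for an observed Rs of 0.5: 0.06 to 0.78 at n = 20, and −0.21 to 0.86 at n = 10.

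Intervals of this width carry information that a yes-or-no verdict at 0.05 hides.

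**The case against.** The strongest reply is that nothing here is contradictory. A nominal 0.05 level is not a confirmatory claim. The protocol does not use the word confirmatory, claims no error control across tests and attaches no decision to a p-value. It calls the study a pilot in the summary, the scientific background, Number of patients and Calculation of case numbers, the last of these shortly before the Statistics section. How p-values are read, and whether intervals are given, may also be settled in a statistical analysis plan that is not at hand.

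Much of this stands. The pilot label is plain, unadjusted testing is acceptable in a pilot, and a missing multiplicity procedure is no finding here. What remains is a sentence that the protocol does contain and that covers all analyses. An analysis plan that treated p-values as descriptive would have to depart from it.

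It can also be said that means and standard deviations are reported whatever the p-value, and that a reader could build an interval from them. This is true for the comparison of separate groups. It is not true for the change within the 10 patients examined twice, because the standard deviation of the change cannot be recovered from the two visits' standard deviations alone.

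A reader might go further and infer that parameters will be picked for later studies because p fell below 0.05, so that inflated effects would be carried forward and the next study would be too small. The documents do not support this. No section selects parameters by p-value, and the only forward-looking sentence is hedged: "The potentially quantifiable differences in ULM could be used in the future as markers to predict nephropathy".

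**Conclusion.** The point holds as a minor one. The rule in the Statistics section is badly matched to the protocol's own aim, for two reasons. Applied to at least 11 unranked primary parameters with no true effect, it gives about a 13% to 30% chance of at least one significant primary result per comparison, with 43% as the ceiling. And a mean, a standard deviation and a verdict leave the effect sizes without an interval.

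The percentages rest on an assumed comparison of 10 against 20 and on assumed correlations of 0.9 to 0.5. More comparisons per parameter, or parameters beyond the 11 named, would raise them. The mismatch between rule and aim does not depend on these assumptions.

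A reader might also infer that the protocol must control the family-wise error rate or name a single primary parameter. That does not follow: an exploratory pilot needs neither, provided its p-values are presented as exploratory.

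**What to change.** Replace the last sentence of the Statistics section with:

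> All analyses are exploratory; p-values are unadjusted and descriptive. Group differences, within-patient changes and Spearman correlations are reported with 95% confidence intervals for every parameter examined, whatever the p-value.

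No multiplicity adjustment is required.

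**Cost.** One or two sentences and slight extra analysis; no additional patients, examinations or time. The downside should be accepted openly: no result of this pilot can be claimed as confirmed, and the reported intervals will look wide (about ±0.79 SD for 10 against 20, and ±0.72 SD of the change for the 10 pairs). That width reflects the size of the study and is there whether or not it is reported.
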